All subjects will take blinded study medication in the morning and evening, with or without food, for 84 consecutive days. Following the 84-day blinded dosing period, all subjects will take open label CCX140-B for an additional 84 days at the highest dose under evaluation, currently planned to be 15 mg twice daily. If the Sponsor, with the advice of the unblinded Data Monitoring Committee (DMC), determines that 15 mg twice daily exceeds the maximum tolerated dose, then the dose administered during the open label period will be adjusted downward from the planned dose to the highest dose that is still under evaluation. There will be a 28-day follow-up period after completion of treatment.

During the treatment period, eligible subjects will visit the study center on Study Days 1, 8, 15, 29 (Week 4), and Weeks 8, 12 (primary endpoint), 13, 16, 20, and 24 for study procedures including interval history, physical examination and vital signs, ECG, study questionnaires, and collection of blood and urine. Subjects will discontinue study drug as of Study Day 169 (Week 24), and will return for a follow up visit on Week 28. When feasible, upon discontinuation of treatment for any reason a sample of whole blood should be collected for assessment of elimination 2, 7 and 14 days after the final dose of CCX140-B (or placebo).

For assessment of adverse events of special interest, study procedures will include

- Complete blood count with differential, morphology assessment, reticulocyte count, hemoglobin, LDH and total and direct bilirubin, to assess early evidence of hemolysis;
- The AIDS Clinical Trials Group Brief Peripheral Neuropathy Screening Tool (ACTG-BPNST), to assess early evidence of neuropathy;
- Monitoring for adverse events of infection;
- Alkaline phosphatase, ALT, AST and total and direct bilirubin; to assess for evidence of drug induced liver injury.

For assessment of pharmacokinetics, study procedures will include

- **Seven** blood samples collected over 6 hours on Study Day 1 and Study Day 15 to assess AUC₀₋₆ following the first administration of study drug, and at steady state;
- Assessment of C_{min} at intervals to ensure that exposure is within the projected range, with adequate safety margin based on the NOAEL established in preclinical toxicology;
- Upon discontinuation of treatment for any reason, collection of blood at 2 days, 7, days and 14 days following discontinuation to assess elimination kinetics.

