The changes in RBC parameter findings are likely translatable to humans, but are monitorable, reversible, and there was an acceptable safety margin across all species (see below). To ensure early detection of **changes in RBC parameters** in the Phase 2 clinical trial, blood samples will be drawn at baseline, at 6 hours following administration of the first dose, at Study Days 8, 15 and 29, then at every 4 week intervals throughout the treatment and follow up period for assessment of complete blood count, reticulocyte count and bilirubin.

Neuropathy findings in dogs are likely species-specific with a higher safety margin than **the changes in RBC parameters**, however reversibility was incomplete and the mechanism is unknown. Subjects in the Phase 2 study will be monitored for adverse events related to the nervous system, and will be **examined for vibration-sense deficits and** evaluated for early symptoms using a questionnaire validated for early detection of peripheral neuropathy in studies of patients with HIV infection.

The NOAEL in the 26-week rat studies of 15 mg/kg/day (based on reversible **changes in RBC parameters**) was associated with systemic AUC₀₋₂₄ total plasma exposures to CCX140 of 464.6 and 493.7 $\mu\text{g}\cdot\text{hr}/\text{mL}$, for males and females, respectively. Thus, for dose escalation in human subjects, exposures to CCX140 should not exceed total plasma AUC₀₋₂₄ exposures of 465 $\mu\text{g}\cdot\text{hr}/\text{mL}$, or total C_{max} concentrations of 32 $\mu\text{g}/\text{mL}$.

Results from all the safety and toxicology studies support repeated dosing of CCX140-B to humans up to predicted exposure parity with the 26-week rat NOAEL levels. The NOAEL in the 26-week rat study was associated with systemic exposure to CCX140 which was approximately 3- to 4-fold the predicted human exposure with a 15 mg twice daily (b.i.d.) dose of CCX140-B.

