4.2.1. Stopping Guidelines

An independent Data Monitoring Committee (DMC) will be responsible for reviewing safety data throughout the course of the study. Among other responsibilities, the DMC is tasked with implementing dose modification guidelines to assure the safety of all study participants.

Guidelines will be defined for stopping the study, halting enrollment or halting treatment based on safety events occurring in more than 1 subject. General dose modification guidelines for individuals are provided below.

Table 2: Dose Modification Guidelines for Single Subjects

| Assessment | Event | Timing | Response |
|---------------------------------------|---|--|-------------------------------------|
| Serum Creatinine | 50% increase from baseline value | If confirmed by repeat measurement after 2 weeks | Discontinue treatment with CCX140-B |
| Urine Protein:Creatinine ratio (UPCR) | If baseline UPCR < 6.0 g/g an increase of >3.0 g/g; if UPCR \geq 6.0 g/g an increase of 50% | If confirmed by repeat measurement after 2 weeks | Discontinue treatment with CCX140-B |

| Assessment | Event | Timing | Response |
|-----------------------------------|--|--|--|
| ALT, AST | ALT or AST ≥ 8 x ULN | Retest within 72 hours (ALT, ASP, ALP and Total Bilirubin should all be re-tested) | If confirmed, discontinue treatment with CCX140-B |
| ALT, AST | ALT or AST ≥ 5 x ULN for more than 2 weeks | Retest within 72 hours and then 2-3 times per week (ALT, ASP, ALP and Total Bilirubin should all be re-tested) | If confirmed, discontinue treatment with CCX140-B |
| ALT, AST, Total Bilirubin and INR | ALT or AST ≥ 3 x ULN and either Total Bilirubin > 2 ULN or INR > 1.5 | Retest within 72 hours (ALT, ASP, ALP, Total Bilirubin and INR should all be re-tested) | If confirmed, discontinue treatment with CCX140-B |
| ALT, AST | ALT or AST ≥ 3 x ULN with the appearance of fatigue, nausea, vomiting, right upper quadrant pain or tenderness, fever, rash and /or eosinophilia ($>5\%$) | | Discontinue treatment with CCX140-B |
| LDH | LDH ≥ 2 times upper limit of normal, and confirmed to not be related to specimen handling | Halt treatment then reassess after 2 weeks | If within normal range, continue to treat at reduced dose, defined as the next lower dose. Otherwise, contact Medical Monitor to discuss next steps |

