| Anemia | Hemoglobin reduced from baseline by ≥ 2 g/dL and deemed clinically significant by the PI | Halt treatment then reassess after 2 weeks | If normal, continue to treat at reduced dose, defined as next lower dose. Otherwise, contact Medical Monitor to discuss next steps |
| Reticulocyte Count | Increase from baseline in reticulocyte count by ≥ 2 units (% of RBC) that is not otherwise explained | Halt treatment then reassess after 2 weeks | If within normal range for the hematocrit, continue to treat at reduced dose, defined as next lower dose. Otherwise, contact Medical Monitor to discuss next steps |

| Assessment | Event | Timing | Response |
|-------------------------------------|---|--|---|
| Peripheral Neuropathy | ≥ moderate symptoms limiting (limiting instrumental activities of daily living) or asymptomatic (based on diagnostic evaluation only) and deemed clinically significant by the PI | Halt treatment then reassess after 2 weeks | Contact Medical Monitor to discuss next steps |
| Other Clinically Significant Events | Any adverse events assessed as moderate, related to study drug, and clinically significant | Halt treatment then reassess after 2 weeks | Contact Medical Monitor to discuss next steps |

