### 3.6.1 Adverse Events (AEs)

An overview of AEs will be provided including counts and percentages of subjects (and event counts) with the following:

- Any TEAEs (overall and by maximum severity)
- Any study drug related TEAEs (overall and by maximum severity)
- Any treatment-emergent serious AEs (TESEAEs)
- Any TEAEs leading to discontinuation of study drug
- Any AEs leading to death

Counts and percentages of subjects (and event counts) will also be presented by system organ class (SOC) and preferred term (PT) using the Medical Dictionary for Regulatory Activities (MedDRA) Version 20.1 any TEAEs and TESEAEs for 3 Safety Populations separately. Counts and percentages of subjects (and event counts) will also be presented by PT in decreasing frequency for any TEAEs and TESEAEs for 3 Safety Populations (see 3.2.4 for definitions) separately.

TEAEs for the Safety Population in each period are defined as an event with a start date on or after the first study drug treatment in each period and up to the final observation in each period. Treatment periods for analysis of adverse event are defined in Section 3.2.4. TEAEs for the All CCX140-B Treated Population are defined as an event with a start date on or after the first dose of CCX140-B up to the final observation.

Listings will be presented specifically for SAEs and TEAEs leading to discontinuation of study drug.

The severity of AEs was assessed by the investigator using the following protocol definitions:

- Mild (Grade 1): no limitation of usual activities
- Moderate (Grade 2): some limitation of usual activities
- Severe (Grade 3): inability to carry out usual activities
- Life-threatening (Grade 4): an immediate risk of death
- Death (Grade 5)

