### *3.6.2 Clinical Laboratory Tests*

Laboratory results and change from baseline will be summarized for each treatment group by visit using descriptive statistics. Summaries will be limited to values assessed by the Central Laboratory. Shift tables from baseline to subsequent study visits will also be generated. Counts and percentages of laboratory values outside the normal reference range will be summarized in the double-blind period and open-label period respectively.

Listings of laboratory values collected at local laboratories will be provided. Laboratory values outside the reference ranges will be flagged in the listings.

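### The SAP plans no by-arm count of subjects who reach the protocol's Table 2 laboratory limits, and no grouping of its special-interest adverse events: a cheap improvement to the safety tables

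*Protocol*

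**What the plan says.** **Topics.** The Synopsis and Protocol section 4 introduce a list with "For assessment of adverse events of special interest, study procedures will include". Blood counts, reticulocytes, LDH and bilirubin serve haemolysis; the ACTG-BPNST serves neuropathy; adverse-event monitoring serves infection; liver enzymes and bilirubin serve liver injury. Neither place gives a case definition or a term list.

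**Reason for interest.** On the animal red-cell findings, Protocol 2.4 states: "The changes in RBC parameter findings are likely translatable to humans". Safety and tolerability is the primary safety objective in both documents.

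**Limits.** Three Table 2 rows in Protocol 4.2.1 halt treatment on a haemolysis-type result:
- haemoglobin: "Hemoglobin reduced from baseline by ≥ 2 g/dL and deemed clinically significant by the PI"
- reticulocytes: "Increase from baseline in reticulocyte count by ≥ 2 units (% of RBC) that is not otherwise explained"
- LDH: at least "2 times upper limit of normal, and confirmed to not be related to specimen handling"

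The liver rows use multiples of the upper limit of normal (ULN). One of them combines ALT/AST with bilirubin or INR.

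**Planned outputs.** SAP 3.6.1 starts: "An overview of AEs will be provided including counts and percentages of subjects (and event counts) with the following". Its action-taken row covers discontinuation of study drug. Events are then tabulated by system organ class and preferred term. SAP 3.6.2 plans laboratory results and change from baseline by arm and visit, and shift tables. It adds: "Counts and percentages of laboratory values outside the normal reference range will be summarized in the double-blind period and open-label period respectively". SAP 3.1.4 gives the descriptive statistics as n, mean, median, SD, minimum and maximum. SAP 3.6.6 summarises ACTG-BPNST change by arm and visit. The term adverse event of special interest does not occur in the SAP.

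**The concern.** The protocol says which results are serious enough to interrupt drug. The natural safety question for each arm is how many subjects had such a result, and no planned table answers it directly. The shift tables and out-of-range counts work on reference ranges, whereas the haemoglobin and reticulocyte limits are changes from baseline. The change summaries use the right scale but describe a distribution, not a number of subjects. A haemolysis picture may also be spread over several preferred terms. Under the three haemolysis rows the first response is a halt, possibly followed by a lower dose, and neither action has a row in SAP 3.6.1.

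At stake is how clearly the report describes the primary safety objective. Protocol 6.4 projects total exposure on 15 mg twice daily at about 2-fold that of 15 mg daily in volunteers, and 3.07-fold that of 10 mg daily in diabetic nephropathy.

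**Working it through.** The documents give no precision or power figure for safety, so there is none to reproduce. The check asks what each planned display would show.

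**1. Haemoglobin in a shift table.** Inputs: a fall of 2.0 g/dL (Table 2) and an entry exclusion below 8 g/dL (Protocol 5.3, criterion 16). Assumptions: low/normal/high categories, a lower limit (LLN) of 11.5 to 13.5 g/dL and an ULN of 15.5 to 17.5 g/dL, because neither document gives categories or ranges. A fall of 2.0 changes category only if LLN ≤ baseline < LLN + 2.
- With a range of 12 to 16: 15.0 to 13.0 is normal to normal; 10.0 to 8.0 is low to low; only baselines from 12.0 to 13.9 shift.
- On a 0.1 g/dL grid of baselines from 8.0 to the ULN, the no-shift share is:

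| Range (g/dL) | No shift / grid values | Share |
|---|---|---|
| 11.5–15.5 | 56/76 | 74% |
| 12–16 | 61/81 | 75% |
| 13–17 | 71/91 | 78% |
| 13.5–17.5 | 76/96 | 79% |

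These are shares of grid values, not of patients. The patient share depends on the baseline distribution, which is unknown.

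**2. Reticulocytes and LDH.** Assume a reticulocyte lower limit of 0.5%. With an upper limit of 1.5% or 2.0%, any in-range baseline plus 2 units leaves the range. With 2.5% it stays in range only from a baseline of 0.5%, and with 3.0% only from 1.0% or less. LDH at 2 × ULN is always out of range, so it shifts unless baseline was already high. ALT/AST at 3 × ULN or more behaves the same way. The masking is therefore clear for haemoglobin, marginal for reticulocytes, and absent for LDH and liver enzymes unless baseline is high.

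**3. Change-from-baseline summary.** Ten subjects in an arm; k fall by 2.0 g/dL and the rest do not change:
- k = 1: mean -0.2, median 0, minimum -2.0
- k = 3: mean -0.6, median 0, minimum -2.0

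The minimum shows that a fall of trigger size occurred. The mean does not fix the number: one fall of 2.0 plus nine falls averaging 0.44 also gives a mean of (-2.0 - 9 × 0.444)/10 = -0.6. The statistics limit the possible count but do not report it.

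**4. Out-of-range counts.** As worded, these count values, not subjects. A value just above ULN and one at 8 × ULN count alike. No display joins ALT/AST with bilirubin or INR in the same subject.

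**5. Unscheduled tests.** Table 2 calls for retests within 72 hours or after 2 weeks, which often fall between visits. The visit windows in SAP 3.1.2 are for efficacy, so the place of these tests in by-visit safety summaries is not stated. SAP 3.6.2 lists local-laboratory values but does not summarise them.

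**6. What a count could show with 10 per arm.** With 0 events in n, the upper exact 90% limit is 1 - 0.05^(1/n): 25.9% for n = 10, and 9.5% for n = 30 (pooled active). The intervals are 0.5% to 39.4% for 1/10 and 8.7% to 60.7% for 3/10. The chance of at least one case among 10, 1 - (1 - p)^10, is 40%, 65% and 89% at true rates of 5%, 10% and 20%.

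**The case against.** The strongest reply is that the plan already covers most of this. SAP 3.6.2 puts change from baseline by arm and visit first, with minimum and maximum. That is the scale Table 2 uses for haemoglobin and reticulocytes. Neuropathy has its own by-arm summary, and infections and liver or blood events appear in the class and term tables. Section 7 of the SAP lists all data, and with 10 per arm a reader could count by hand. The protocol attaches tests to its four topics but promises no separate analysis of them. The data monitoring committee's charter holds its own triggers, and the programming specifications are a separate document; neither was available for this review.

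Most of this stands. A reader might infer that laboratory data are shown only against reference ranges, or that the four topics get no by-arm analysis. SAP 3.6.1, 3.6.2 and 3.6.6 contradict both. A reader might also infer that the report could not say how many subjects reached a limit. The listings would allow it; the gap is that no planned table does so.

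A further objection concerns the remedy: a laboratory count is not a count of Table 2 events. Haemoglobin needs the investigator's judgement, reticulocytes the absence of another explanation, LDH a check of specimen handling, and the liver rows confirmation or duration. This is correct and governs how the table must be labelled. It does not remove the value of the count.

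**Conclusion.** The point holds as a cheap improvement, not as an error or a broken commitment. SAP 3.6 has no grouping by special-interest topic, no by-arm number of subjects reaching the Table 2 laboratory limits, no joint ALT/AST with bilirubin or INR display, and no row for halts or dose reductions.

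The size can be stated only conditionally. Under assumed reference ranges and low/normal/high categories, a 2 g/dL haemoglobin fall leaves the category unchanged from 74% to 79% of the baseline values examined. The planned change summary shows the largest fall but not how many subjects had one. It would go too far to say that a haemolysis signal as such would show as no shift: LDH at its limit always leaves the range, and reticulocytes usually do under the assumed ranges. Nor can the gap be sized by a between-arm test, because SAP 3.6 plans none and 10 per arm would not support one.

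**What to change.** Change the analysis only. Add to SAP 3.6, by arm and by period (SAP 3.2.4), the number and percentage of subjects whose worst post-baseline value, including unscheduled tests, meets the laboratory component of these existing Table 2 criteria:
- haemoglobin fall of at least 2 g/dL
- reticulocyte rise of at least 2 units
- LDH at least 2 × ULN
- ALT or AST at least 5 × ULN, and at least 8 × ULN
- ALT or AST at least 3 × ULN with bilirubin above 2 × ULN or INR above 1.5

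Label the table as laboratory components only, because several rows also need judgement, confirmation or duration. State which baseline applies in the open-label period and whether local-laboratory values count. Note that INR is not scheduled at Weeks 2, 8 and 20.

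Add counts of subjects with a drug halt and with a dose reduction. Add one row for each of the four topics, from a list of preferred terms fixed before database lock. For the blinded period give descriptive 90% intervals; the exact method that SAP 3.4.1 uses for response rates would serve.

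The cost is one or two tables and the term list. The laboratory data are already collected. The drawback is wide intervals with 10 per arm, so the table describes a signal and does not test it. No limit or treatment rule in Table 2 is altered.

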2. INTRODUCTION

2.1. Background Information

CCX140-B is an orally administered, selective antagonist of C-C chemokine receptor type 2 (CCR2) that has demonstrated efficacy for reduction of proteinuria in a Phase 2 study in patients with diabetic nephropathy and is currently in development for treatment of patients with focal segmental glomerulosclerosis (FSGS).

Additional limitations of current therapy include significant morbidity and premature mortality ascribable to the neurologic, metabolic and bone toxicity associated with high dose glucocorticoids, renal toxicity associated with calcineurin inhibitors, and to immunosuppression. There is a need for therapeutic approaches that induce and maintain response in a greater proportion of subjects with less toxicity.

2.3. Potential Role of CCR2 in Pathogenesis of FSGS

A potential role for CCR2 in the pathogenesis of FSGS is supported by clinical and histopathologic observations in subjects with renal disease, and findings with *in vitro* studies and *in vivo* mouse models of FSGS.

CCR2 is a major driver of monocyte migration and activation, and has been shown to mediate renal interstitial inflammation and tubular atrophy in chronic renal diseases by recruiting monocytes to the renal interstitium (Yadav et al; 2010). Increased urinary levels of MCP-1, the ligand for CCR2, is associated with increased interstitial macrophage infiltration in subjects with chronic kidney disease (Eardley et al, 2006) and with increased degree of proteinuria in children with FSGS (Wasilewska, et al, 2011). There is a well-characterized DNA polymorphism (MCP1 2518 A/G) that has been associated with elevated MCP-1 levels and greater risk for development of renal failure in FSGS, as well as in IgA nephropathy, diabetic nephropathy and lupus nephritis (Besbas et al, 2015).

In vitro experiments support a role for the CCR2/MCP-1 pathway in the purported disease acceleration role ascribed to proteinuria. Specifically, it is reported that tubular epithelial cells release MCP-1 (CCL2) when exposed to serum proteins on the apical side (Burton et al, 1999).

In vivo, targeting the MCP-1/CCR2 system in preclinical models of **chronic kidney disease** (CKD) demonstrates benefit. MCP-1 deficient mice are resistant to the development of albuminuria following diabetes induction by streptozotocin and this protective phenotype is marked by a lack of monocyte recruitment into the glomeruli (Chow et al., 2006). MCP-1 deficiency also prevents diabetic *db/db* mice from developing albuminuria (Chow et al., 2007). Pharmacological treatment with a CCR2 antagonist prevents the onset of albuminuria in *db/db* mice and this benefit correlates with a lack of monocyte recruitment to the glomeruli and amelioration of histological damage (Kang et al., 2010). ChemoCentryx conducted an extensive series of preclinical efficacy studies with CCX140-B and surrogate CCR2 antagonists. Efficacy was observed in mouse models of diabetic, non-diabetic nephropathy and in models with features of FSGS induced by partial nephrectomy or by exposure to Adriamycin (ADR). Rapid and significant reduction in proteinuria as assessed by measurements of urinary albumin excretion rate (UAER) and urinary albumin:creatinine ratio (UACR) was observed in all animal models, the reduction in proteinuria are sustained throughout the duration of the studies. Histological parameters were also improved by treatment with CCR2 inhibitors and in combination with RAAS blockade. These histological parameters include reduced glomerular hypertrophy, mesangial expansion, glomerular sclerosis, and increased tubular and glomerular integrity. In addition, histopathology reveals preservation of glomerular architecture and restoration of normal tubular appearance with CCR2 blockade in the 5/6 nephrectomy mouse model. The presence of intra-glomerular CCR2 positive cells has been demonstrated in the animal models (PC0684_140). Moreover, renal protective effects are associated with CCR2 inhibition in the FSGS models. Notably, the number of podocytes per glomerulus is significantly higher with CCR2 inhibitor therapy than in vehicle-treated matched controls (See Investigator's Brochure).

Ex vivo, evidence for a role for CCR2 in FSGS in humans comes from unpublished studies conducted by ChemoCentryx. Expression of CCR2 protein was assessed using immunohistochemistry methods in renal biopsies from normal kidney and from subjects with

primary FSGS. Both showed expression of CCR2 in cells implicated in pathogenesis, including parietal epithelial cells, tubular epithelial cells and infiltrating macrophages.

Difference in expression between healthy and diseased kidney was observed in the tubular epithelium, consistent with prior data showing that proteinuria induces CCL2 (MCP-1, the ligand for CCR2) expression in tubules (Burton et al; 1999).

Finally, support derives from the demonstration that CCX140-B was associated with clinically meaningful reduction in proteinuria in a Phase 2 study in subjects with diabetic nephropathy (de Zeeuw, et al., 2015), as summarized in [Section 2.4.1](#). The pathogenic mechanisms that contribute to proteinuria and progressive renal dysfunction in diabetic nephropathy are shared, at least in part, with mechanisms in FSGS (Jefferson et al., 2008). Specifically, a decrease in podocyte number has been shown in subjects with both type I and type II diabetes mellitus, reduced podocyte number may precede the onset of clinically detectable albuminuria and/or proteinuria by several years, foot process effacement is observed, and experimental and clinical studies have shown a direct correlation between the magnitude of proteinuria and the extent of effacement and decrease in podocyte number. Further, as in FSGS, increased glomerular proteinuria leads to enhanced tubular cell uptake of protein, leading to complement activation, tubulointerstitial inflammation and release of fibrogenic growth factors and inflammatory cytokines.

These observations support the rationale that selective CCR2 inhibition with CCX140-B may provide therapeutic benefit in subjects with FSGS.

